In 2022 a meta-analysis performed by (**Grawish et al., 2022**)⁽²³⁾ indicated that DDM as a regenerative biomaterial has potential roles in tissue regeneration. However, in order to confirm these trials, further well-designed analyses are needed, and evaluation of adverse events in observational studies is also needed.

To our knowledge, DDM has not been investigated as scaffold in regenerative endodontics for permanent teeth.

Several studies were evaluate the regenerative effect of DDM at dentin-pulp complex through direct pulp capping technique, and it was found to possess the ability to activate the odontogenic differentiation of stem cells resident in the pulp tissues and induce reparative dentin formation. DDM also considered for alveolar ridge, maxillary sinus floor augmentations, socket preservation, furcation perforation repair, guided bone, and bioroot regenerations as well as bone and cartilage healing ⁽²³⁻²⁷⁾.

Hence, this study will be designed to evaluate regenerative effect of Demineralized Dentin Matrix as a scaffold in comparison to conventional blood clot in immature permanent teeth.

II. The null hypothesis

The null hypothesis is that there are no significance differences in the clinical and radiographic outcomes of regenerative endodontic of non-vital immature permanent teeth following the use of DDM in comparison to a blood clot scaffold.

III. Aim of the study

This study aims to:

Compare the clinical and radiographic outcomes of demineralized dentin matrix scaffold to blood clot scaffold in immature permanent incisors with non-vital pulps for one year.

IV. PICOTS

P: Patients ranging age 7–13years

I: Demineralized Dentin Matrix as a scaffold in Regenerative endodontic procedure

C: Blood clot scaffold Regenerative endodontic procedure

O: Clinical and radiographic success.

T: One year

S: outpatient's clinic of the Pediatric Dentistry and Dental Public Health Department, Faculty of Dentistry, Ain Shams University.

V. Methodology:

i. Study design

A Randomized, Controlled trial with 1:1 allocation ratio

ii. Sample size estimation

A power analysis was designed to have adequate power to apply a two-sided statistical test of the null hypothesis that there is no difference would be found between different groups. By adopting an alpha level of (0.05) a beta of (0.2) i.e. power=80% and an effect size (d) of

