(1.51) calculated based on the results of a previous study ⁽²⁵⁾. the predicted sample size (n) was a total of (24) cases (i.e. 12 cases per group). Sample size was increased by 20% to compensate for possible dropouts during follow-up intervals to be (30) cases (i.e. 10 cases per group). Sample size calculation was performed using G*Power version 3.1.9.7⁽²⁸⁾

iii. Assignment of intervention:

a. Randomization and Allocation concealment.

1- Type: block Randomization, with blocks numbers of 10 and 1:1:1 allocation ratio in to 3 groups

Group I: DDM (study)

Group II: (control) blood clot

Group III: (+ control) blood clot with collagen

2- Sequence generation: the most senior supervisor will generate the sequence of random numbers using online randomization (www.random.org).

Allocation concealment and implementation:

Allocation concealment will be ensured by preparing opaque envelopes containing one number from the generated random sequence for assigned group. The most senior supervisor will select an envelope and reveal the treatment group at the final regeneration visit.

b. Blinding:

double blind study, participants, outcome assessors, statistician will be blinded.

iv. Study setting

This study will be conducted at the Outpatients Clinic at the Department of Pediatric Dentistry and Dental Public Health, Faculty of Dentistry, Ain Shams University.

ii. Study methodology

ethical regulation:

The study protocol will be submitted to the Research ethics committee, Faculty of Dentistry, Ain Shams University for approval.

V. Population

All parent or legal guardian fulfill the eligible criteria will be signed an informed consent before beginning any procedure, explaining detailed treatment procedures, the possible outcomes, comprehensive discussions of the risks, complications, alternative treatment options, follow-up period needed, and sequel of no treatment⁽⁸⁻¹⁴⁾.

Inclusion criteria:

- (1) Age 7–13 years at the time of enrolment.
- (2) Provision of informed consent by one parent or legal guardian.
- (3) At least one immature permanent anterior tooth diagnosed with irreversible pulpitis or pulp necrosis with or without periapical lesions.
- (4) Restorable teeth.
- (5) Compliant patient/parent.
- (6) Patients not allergic to medicaments and antibiotics necessary to complete procedure (ASA 1 or 2).
- (7) Radiologic evidence of open apices (Teeth are considered immature when a minimum of 1 mm apical foramen width is evident)

Exclusion criteria

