- (1) Teeth with root fractures or split roots.
- (2) Presence of root resorptions.
- (3) Presence of periodontal pockets.
- (4) Developmental anomalies
- (5) Presence of periapical radiolucency more than 10 mm
- (6) Tooth with class III mobility.

vi. Clinical Procedures

a. Screening Recruitment

Patients attending the outpatient's clinic of the Pediatric Dentistry and Dental Public Health Department, Ain Shams University will be screened for eligibility. Only patients who met the inclusion criteria and sign the informed consent will be conveniently enrolled in the study until

the predetermined sample size is reached. All examination procedures will be done by the same operator to ensure standardization.

b. Informed Consent

A signed informed consent from parent or legal guardian, and an oral assent to the child, as outlined by the Research Ethics Committee, Faculty of Dentistry, Ain Shams University will be obtained before the conduction of the study.

Grouping:

Eligible immature anterior teeth will be randomly allocated in two groups:

Group I: 10 teeth will be treated with demineralized dentin matrix as scaffold in regenerative endodontic procedure.

Group II: 10 teeth will be treated with conventional regenerative endodontic procedure (blood clot scaffold).

Group III: 10 teeth will be treated with regenerative endodontic procedure (bloodclot and collagen scaffold).

Clinical procedures:

Pre-operative periapical radiograph and cone beam computed tomography CBCT will be taken on the selected non-vital tooth in each child before the beginning of the regenerative endodontic treatment procedure (29, 30).

RET will be carried out according to ASE⁽⁸⁾

First Appointment

- Local analgesia will be delivered (2% lidocaine with 1:100,000 adrenaline).
- Following rubber dam isolation and access cavity preparation, pulp tissue extirpation/debridement
- The root canal system will be minimally instrumented.
- Copious irrigation will be performed, gently with 20ml NaOCl (1.5% NaOCl (20mL/canal, 5 min) using 0.3mm gauge single side vented needles, adjusted 3 mm short of the apex.
- then canal will be irrigated with EDTA (20 mL/canal, 5 min), with irrigating needle that will be positioned about 1 mm shorter than the root end, to minimize cytotoxicity to stem cells in the apical tissues, followed by a final rinse 20 mL sterile saline .

- Canals will be dried with paper points.

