double antibiotic paste, ciprofloxacin (Ciprocin 250mg tablets) and Metronidazole (Flagyl 500mg tablets) in a 1:1 ratio will be mixed with sterile distilled water in a 3:1 ratio, then will be introduced into the root canal systems using 18 G hypodermic needle and will be packed gently down the root canal using a hand plunger, ensuring that there will be no remains coronal to CEJ

- A sterile dry cotton pellet will be placed over the paste after which the tooth will be sealed with 3-4mm of a temporary restorative material.
- Patient will be dismissed for 2 week

Second Appointment (two week after 1st visit)

- Response to initial treatment will be assessed. If there are signs/symptoms of persistent infection, additional treatment time with antimicrobial.
- Local Anesthesia without vasoconstrictor will be administered; dental dam isolation will be achieved.
- Copious gentle irrigation will be performed with 20ml of 17% EDTA, followed by a final rinse 20 mL sterile saline.
- Canals will be dried with paper points.

In group I: teeth will be treated with demineralized dentin matrix as scaffold in regenerative endodontic procedure

Teeth, in this group, will be anaesthetised using a local anaesthetic without vasoconstrictor. Demineralized dentin matrix will be introduced inside the root canal and bleeding will be created into root canal by over-instrumentation by rotating K-file at 2 mm past the apical foramen with the goal of having the entire canal filled with blood to the level of the cemento-enamel junction.

A lightly moistened sterile cotton pellet will be placed into the canal, 3-4 mm apical to the CEJ, for 7-10 minutes to allow blood clot formation.

Placement of the bioactive and restorative materials: A bioactive material such as tricalcium silicate will be placed over the blood clot as a capping material. A 3-4 mm layer of glass ionomer will be gently placed over the capping material.

Followed by resin composite restoration ⁽¹⁶⁾.

In group II: teeth will be treated with conventional regenerative endodontic procedure (blood clot scaffold).

Teeth, in this group, will be anaesthetised using a local anaesthetic without vasoconstrictor. Bleeding will be created into root canal by over-instrumentation

A lightly moistened sterile cotton pellet will be placed into the canal, 3-4 mm apical to the CEJ, for 7-10 minutes to allow blood clot formation.

Placement of the bioactive and restorative materials as mentioned above.

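### The blocking rule does not say whether 10 is the block size or the number of blocks: a block of 10 cannot be 1:1:1, and ten blocks force fixed blocks of three

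*Protocol*

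**What the plan says.** The Protocol, under Randomization and Allocation concealment, specifies "block Randomization, with blocks numbers of 10 and 1:1:1 allocation ratio in to 3 groups". Nothing there says what the 10 counts.

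The figures that bear on it are these:

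- **Total and group size.** Sample size estimation ends with the total raised "to be (30) cases (i.e. 10 cases per group"). Grouping repeats 10 teeth for each of three groups, for example "Group II: 10 teeth will be treated with conventional regenerative endodontic procedure".
- **Ratio.** Study design has "A Randomized, Controlled trial with 1:1 allocation ratio", against "1:1:1 allocation ratio in to 3 groups" in the randomisation section. Grouping announces two groups and then lists three. The three-group ratio is used here because it matches the 30 and the three lists of 10.
- **Envelopes.** They are described as opaque. Sealing, numbering and order of use are not mentioned. The most senior supervisor generates the sequence, selects the envelope and reveals the group at the final regeneration visit.
- **Blinding.** Participants, outcome assessors and the statistician are listed. The operator is not.
- **Before the reveal.** At the second appointment the response to the first is assessed: "If there are signs/symptoms of persistent infection, additional treatment time with antimicrobial".

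**The concern.** The sentence has two readings, and each has a problem.

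If 10 is the block size, no block can hold the stated ratio, and the protocol has no rule for the left-over place. The planned 10 per group is then not guaranteed.

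If 10 is the number of blocks, the ratio and group sizes work, but every block must have exactly three places. That is the smallest possible block for three arms, it is fixed, and anyone reading the protocol can work it out. The operator can see whether demineralized dentin matrix, collagen or neither goes into the canal. After two teeth of a block have been treated, the third allocation can be inferred.

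What is at stake is concealment of the next allocation while the clinical team still judges whether an enrolled tooth is ready for its final visit. Imbalance is the lesser matter. A second person also could not reproduce the allocation list from the text.

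**Working it through.** **Inputs.** Total 30 and 10 per group (Sample size estimation, Grouping); three arms at 1:1:1 and the figure 10 (Randomization and Allocation concealment); d = 1.51, two-sided alpha 0.05, power 80% and 20% dropout (Sample size estimation).

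**The plan's own total.** A two-sample t-test with d = 1.51 needs 7.97, so 8 per arm. Then 8 × 3 = 24, 24 / (1 − 0.20) = 30, and 30 / 3 = 10 per arm. The 30 is reproduced for three arms. (The bracketed 12 per group alongside the 24 fits only two arms; that does not affect this point.)

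**Reading A: block size 10.**

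- 10 = 3 × 3 + 1, so no block is 1:1:1. The nearest split is 4/3/3, and 30 / 10 = 3 blocks.
- The extra place can fall in any of three arms in each block, giving 3³ = 27 patterns. The frequencies below assume that it falls at random, a rule that the protocol does not state.

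| Totals | Patterns | Share |
|---|---|---|
| 10/10/10 | 6 of 27 | 22% |
| 11/10/9 | 18 of 27 | 67% |
| 12/9/9 | 3 of 27 | 11% |

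- If the extra place is rotated over the arms, the result is always 10/10/10.
- Cost in pairwise t-test power at d = 1.51, before dropout: 0.89 at 10 v 10, 0.87 at 10 v 9, 0.89 at 11 v 9, 0.90 at 12 v 9 and 0.85 at 9 v 9. The loss is small.

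**Reading B: ten blocks.**

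- A 1:1:1 block needs at least 3 places, and 10 × 3 = 30 uses the whole sample. Every block is therefore exactly 3, and the totals are 10/10/10.
- The third place in each block is fixed by the first two: 10 of 30 = 33% certain.
- Best-guess success: (1/3 + 1/2 + 1) / 3 = 0.611, or 18.3 of 30, against 10 of 30 (33%) under simple randomisation.
- These figures assume that the guesser knows the block boundaries and the earlier allocations, and that envelopes are used in sequence.

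**Mixed blocks: four of 3 and three of 6.**

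- Size: 4 × 3 + 3 × 6 = 30. Per arm: 4 × 1 + 3 × 2 = 10.
- A 2/2/2 block has 1 + 1/5 = 1.2 certain places on average: the last always, and the fifth when the last two are the same arm.
- Expected correct guesses in a 2/2/2 block: 1/3 + 2/5 + 1/2 + 8/15 + 3/5 + 1 = 3.37.
- If all sizes and their order were known: certain = 4 × 1 + 3 × 1.2 = 7.6 of 30 (25%). Correct guesses = 4 × 1.83 + 3 × 3.37 = 17.4 of 30 (58%).

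**The case against.** The strongest defence is that ten blocks is the more natural reading of the phrase and the only one that fits every other figure: 30 teeth, three arms, 10 in each. On that reading the scheme does give 1:1:1, and fixed blocks of three are a valid way to get there. This stands. A reader might infer from the figure 10 that the trial cannot deliver its ratio or that planned group sizes are lost. The documents do not support that: it is strict only within a block of 10, rotating the extra place would restore 10/10/10, and the worst split is 12/9/9.

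The second defence is that predictability needs conditions the protocol does not establish. The operator must know the boundaries and the envelopes must be used in order. Since numbering and order of use are not described, free picking is possible, and block order would then be lost. This also stands, so 33% and 61% are upper figures. It does not rescue the text, because under free picking the stated blocking would not be carried out.

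The third is that the group is revealed only at the final regeneration visit, after eligibility, consent, baseline imaging and the first appointment. That largely protects the choice of whom to enrol, so a reader who infers biased enrolment goes too far. What remains is the order and timing in which enrolled teeth reach the final visit. The interval is set at two weeks and extra time is tied to signs or symptoms of persistent infection, which narrows the room for judgement but does not close it.

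**Conclusion.** The concern holds as a defect of specification with a limited route to bias. The sentence leaves the block structure undetermined and each reading has a weakness.

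- Block size 10 is incompatible with 1:1:1 within a block. Overall balance then depends on a rule that is not stated: 10/10/10 always if the extra place is rotated, 22% of the time if it is random. The consequence for power is small either way.
- Ten blocks give exact balance, but through fixed blocks of three that can be deduced from the protocol. Up to 10 of 30 allocations could be known, with 61% best-guess success against 33%, if an unblinded operator knows the boundaries and envelopes are used in order.

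It would be wrong to read this as showing that a third of allocations will be predicted, or that the result will be biased. The documents support only the ceiling, and the size of any bias cannot be estimated from them. The point should be corrected before the first allocation because doing so is nearly free.

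**What to change.** State the block structure without ambiguity. Use permuted blocks whose sizes are multiples of three, in random order and totalling 30, such as four blocks of 3 and three of 6, which gives 10/10/10 with 1:1:1 in every block. This set is an illustration: the sizes and order actually used belong in a restricted document that the operator cannot read until the last tooth is treated, and the protocol should say only that block sizes vary and are concealed. Specify sequentially numbered, sealed opaque envelopes opened in order.

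Concealment does most of the work. With sizes and order known, the mixed scheme would still leave 7.6 of 30 allocations certain and a best-guess rate of 58%, against 10 and 61% for fixed blocks of three.

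The cost is regenerating the list and slightly looser balance within the sequence than with fixed blocks of three. Sample size and final group sizes do not change.

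### The supervisor who generates the random sequence also picks each envelope, with no fixed order of use, so the assignment of enrolled children is not protected

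*Protocol*

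**What the plan says.** Everything on this point stands in the Protocol, section V. Methodology, iii. Assignment of intervention.

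- **Type of randomisation:** "block Randomization, with blocks numbers of 10 and 1:1:1 allocation ratio in to 3 groups".
- **Generation:** "the most senior supervisor will generate the sequence of random numbers using online randomization".
- **Concealment:** "Allocation concealment will be ensured by preparing opaque envelopes containing one number from the generated random sequence for assigned group".
- **Implementation:** "The most senior supervisor will select an envelope and reveal the treatment group at the final regeneration visit".
- **Blinding (item b):** "double blind study, participants, outcome assessors, statistician will be blinded". The supervisor is not on this list.

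No other section adds a safeguard. Sealing, numbering, opening in order, identifying the child on the envelope before it is opened, and keeping a log are not mentioned anywhere.

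**The concern.** Allocation concealment requires that whoever assigns the next patient can neither know nor influence the next allocation. Here the person who made the list also chooses the envelope, for a child whose case is already known, and the verb used is to select rather than to open the next one. Opacity alone does not separate these two roles.

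If assignment could be matched to prognosis, the arms could differ at baseline for reasons other than chance. In a trial of 30 teeth a few such assignments would matter. Without numbering or a log, the investigators would have no record with which to answer a reader who asked whether it had happened.

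**Working it through.** The protocol states no figure for this point, so the check is mainly a comparison of its sections.

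**1. Who knows the sequence, and who assigns?** The generation and implementation items name the same role, the most senior supervisor. The overlap is stated outright and need not be inferred.

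**2. What stands between that knowledge and the assignment?** Only that the envelopes are opaque. The concealment item is in the passive and does not say who fills or holds them. The supervisor would know what a given envelope holds if he or she filled the envelopes, or if they were numbered to match the list. The text neither states nor excludes either condition. The accurate statement is therefore that the assigner may know the allocation.

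**3. What is known about the child when the envelope is chosen?** The implementation item places the step late: "reveal the treatment group at the final regeneration visit". Under Clinical procedures, the periapical radiograph and CBCT are taken before treatment starts, and the response to initial treatment is assessed at the second appointment. Much of the prognostic information is thus available before assignment.

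**4. Is there prognostic variation to act on?** Yes. The inclusion criteria admit teeth with or without periapical lesions, and the exclusion criteria remove only radiolucencies above 10 mm. Eligible teeth therefore range from no lesion up to 10 mm.

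**5. Does blinding repair it?** No. The blinded roles are participants, outcome assessors and statistician. Blinding acts after assignment and cannot undo a steered one.

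**6. Is the block order safe?** A blocked sequence keeps its balance over time only if the envelopes are used in the order generated. The protocol fixes no order, so the block order is not guaranteed. This holds however the stated block specification is read. That specification is itself unclear, because a block of 10 does not divide equally among three groups (10 = 3 × 3 + 1), but that is a separate matter.

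**7. How much can one tooth move the result?** Input: 10 teeth per group (sample size section and Grouping).

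Share of one tooth in an arm's success rate = 1/10 = 0.10 = 10 percentage points.

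This is the most that one tooth can change its arm's rate. It is reached only if steering that tooth changes a failure into a success in that arm, or the reverse.

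**The case against.** The strongest reply is that the protocol does protect something, and that much of the rest is silence.

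- **Enrolment.** Consent and enrolment come before the group is revealed, and nothing says that the supervisor screens, enrols or treats. The Screening section gives all examinations to one operator, and the Confidentiality and Access to data sections distinguish the primary investigator from the supervisors. A reader might infer that concealment fails altogether. The documents do not support that: the enrolment decision has some protection, and the exposed step is assignment.
- **Knowledge of contents.** A reader might infer that the envelopes conceal nothing from the supervisor. That does not follow. Knowing a list does not reveal the content of an unmarked opaque envelope filled by someone else, and the protocol does not say who fills them.
- **Block order.** A reader might infer that the blocks will be broken. The text does not say that envelopes are taken out of order; it only fails to require order. If they were drawn blindly in no order, the allocation would be unsteered, and using all of them would still end at the planned 10 per arm. Lost balance partway through is therefore not a measure of selection bias, and the protocol describes no interim analysis that it would affect.
- **Teeth with persistent infection.** A reader might take these as the obvious candidates for steering. Under Second Appointment, however, they receive further antimicrobial time, so they would normally be treated further before the visit at which the group is revealed.
- **Sealing and numbering.** Their absence from the text is an omission, not a statement that they will not be used.

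These replies narrow the point and are accepted as limits on it. They do not answer the core of it: the role overlap and the unfixed choice of envelope are written rules, and the protocol claims that concealment is secured by them.

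**Conclusion.** The point holds in limited form. The procedure as written leaves the assignment of already enrolled children open to influence by someone who may know the sequence, and it does not guarantee the block order. It is not evidence that allocation will be steered, and no size of bias can be derived from the documents. The only figure available is the ceiling of 10 percentage points of an arm's success rate per tooth, which assumes 10 teeth per arm and a steered tooth whose outcome changes that arm's count.

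This is not a detail that can be left to a statistical analysis plan. Sequence generation and concealment are protocol matters, and this protocol sets a rule for them that does not deliver the concealment it claims. It should be changed, ideally before the first envelope is opened.

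**What to change.** 1. Keep the most senior supervisor as generator of the sequence only.
2. Use sequentially numbered, sealed, opaque envelopes.
3. Have an existing team member who has not seen the list open them in strict number order, still at the final regeneration visit.
4. Write the child's code and the date on the envelope before it is opened.
5. Keep a log of each opening.

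The cost is negligible: numbering, sealing, a log sheet and a reassignment of one task within the present team. Sample size, timing of the reveal and treatment procedures do not change. If the protocol is already in force, the change goes through the ethics committee review that it describes under Protocol amendments.

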Categorical data will be represented as frequency (n) and percentage (%) and will be analyzed using chi square test. Numerical data will be explored for normality by checking the data distribution, calculating the mean and median values and using Kolmogorov-Smirnov and Shapiro-Wilk tests. If the data was found to be normally distributed, it will be presented as mean and standard deviation values and paired t-test will be used for the analysis. If the assumption of normality was found to be violated; the data will be presented as median and range values and will be analyzed using Signed rank test. The significance level will be set at $p \leq 0.05$ for all tests. Statistical analysis will be performed with IBM SPSS Statistics Version 26 for Windows.

VIII. Study timeline

This study will be conducted from October 2023 to October 2024.

X. Patient withdrawal

- Patients who aren't willing to continue in the study will have the right to quit at any time without loss of any benefits.
- Patients who don't comply with the oral hygiene measures given will be excluded from the study and will be offered to continue dental treatment at the departments' outpatient clinic.
- Any adverse event will be recorded and managed promptly. In addition, in failure occurs, the use of the experimental material will be stopped and patients will be treated with another modality.

[figure not shown]
xi. Data management

Patient information will be guarded as confidential information that should never be revealed at all times.

All information will be kept as a hard and soft copy.

xii. Adverse event reporting

Regenerative treatment is not expected to have any adverse side effects on health but if failure occurs in the regenerative treatment, conventional regenerative endodontic treatment will be fabricated.

xiii. Ethics and dissemination

a. Research ethics approval:

This protocol and the template informed consent form contained in Appendix are written following the guidelines outlined by the Research Ethics Committee and Institutional Review Board, Faculty of Dentistry, Ain Shams University.

b. Protocol amendments:

In case of protocol modifications, the Research Ethics Committee and Institutional Review Board, Faculty of Dentistry, Ain Shams University will review and approve the changes of protocol before proceeding and implementation of changes.

c. Informed consent:

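### The protocol contradicts itself on two versus three arms, gives the collagen arm no hypothesis, and reads four unranked primary signs each at p ≤ 0.05

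*Protocol*

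**What the plan says.** The Protocol describes two different designs.

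- Two arms: V.i, Study design, reads "A Randomized, Controlled trial with 1:1 allocation ratio". The Grouping paragraph opens with "Eligible immature anterior teeth will be randomly allocated in two groups". The null hypothesis (II) concerns outcomes "following the use of DDM in comparison to a blood clot scaffold", and the aim (III) and the PICOTS comparator (IV) are limited to the same pair.
- Three arms: V.iii.a, Randomization, reads "1:1:1 allocation ratio in to 3 groups" and labels Group III, blood clot with collagen, a positive control. The list directly under the Grouping sentence has three groups of 10 teeth. The clinical procedures section describes a separate Group III procedure.

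The outcome table (f, Outcome measurement) gives the primary outcome as four separate items: pain, pain on percussion, pathological mobility and a gingival pocket item. It neither ranks nor combines them. Section VII assigns categorical data to a chi-square test, without saying whether it is an overall or a pairwise test. "The significance level will be set at" p ≤ 0.05 for all tests.

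**The concern.** A third of the teeth go to an arm whose only stated role is a label. A reader of the results could not tell whether a collagen comparison was planned, or what it was meant to show.

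The second part concerns the pair that the null does name. It can be tested on four primary signs, each at the full 5%, and nothing says which sign decides. A significant difference on any one of them could be reported as rejecting the null, so the error rate of the main claim need not be the 5% used for sizing. A detailed multiplicity procedure is often left to a statistical analysis plan. Here, however, the protocol itself fixes one threshold for every test, so the rule is stated and not merely absent.

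**Working it through.** **1. The sizing, reproduced.** Inputs from Protocol V.ii: "By adopting an alpha level of (0.05) a beta of (0.2) i.e. power=80"%, a "two-sided statistical test of the null hypothesis", effect size d = 1.51, total 24, then 30 after a 20% dropout allowance.

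- A two-sample t-test at two-sided 0.05 with d = 1.51 (noncentral t) needs 8 per arm, with power 0.802.
- 3 × 8 = 24; 24 / 0.8 = 30; 30 / 3 = 10 per arm.

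The totals therefore fit three arms, sized for a single pair at an unadjusted 0.05. The label of 12 per group fits only two arms (2 × 12 = 24; 3 × 12 = 36), so the two-versus-three conflict also runs through the sample-size paragraph.

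**2. Ceilings if all tests were independent.** The chance of at least one false positive in k tests at 0.05 is 1 − 0.95^k.

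- Four signs, one pair: 1 − 0.95^4 = 18.5%.
- Four signs, three pairs: 1 − 0.95^12 = 46.0%.

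These are upper figures. Pairs share arms, signs are correlated, and chi-square on 10 teeth per arm is often conservative.

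**3. Simulation for binary signs.** Assumptions: 10 teeth per arm, no true difference, uncorrected Pearson chi-square, four signs with the same event rate, and latent correlation 0 or 0.5 between signs. The protocol gives no event rates, so a range is shown.

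| True event rate | DDM vs blood clot, four signs | One three-group test per sign (4 tests) | All pairs, all signs (12 tests) |
|---|---|---|---|
| 5% | about 0.5% | about 5% | about 1% |
| 10% | about 3.5% | 13–14% | 8–9% |
| 20% | 11–12% | 18–19% | 26–28% |
| 30% | 13–14% | 17–18% | 30–32% |
| 40% | 14–15% | 15–16% | 31–34% |

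**4. Check of the first column.** The simulated error of one chi-square test for one sign, DDM versus blood clot, is 0.0011, 0.0092, 0.0298 and 0.0365 at event rates of 5%, 10%, 20% and 30%. For four independent signs:

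- 1 − (1 − 0.0011)^4 = 0.4%
- 1 − (1 − 0.0092)^4 = 3.6%
- 1 − (1 − 0.0298)^4 = 11.4%
- 1 − (1 − 0.0365)^4 = 13.8%

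These agree with the table.

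**5. After the fix.** One composite compared once between DDM and blood clot gave 2–4% in the same kind of simulation (event rates of 10–40% per sign), which is within the nominal 5%.

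**6. Cost of the alternative.** Suppose the collagen comparisons were to stay confirmatory on one continuous outcome with d = 1.51, using Bonferroni.

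- DDM against each control at 0.025: 10 evaluable per arm (power 0.815); 10 / 0.8 = 12.5, so 13 per arm and 39 in total.
- All three pairs at 0.0167: 11 evaluable per arm (power 0.813); 11 / 0.8 = 13.75, so 14 per arm and 42 in total.

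**The case against.** The strongest reply is that the trial does name its comparison. The null, the aim and PICOTS all point to DDM versus blood clot. A reader might infer from the arm mismatch that no comparison is confirmatory. The documents do not support that: the pair is named, and what is missing is a deciding outcome for it and a role for Group III. A reader might also infer that a collagen result could reject the null. It could not, because that null does not mention collagen. The sizing text speaks more loosely of different groups, but it sets no collagen test.

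The second reply concerns size. The protocol does not say that pairwise tests will be run, so the 12-test family is only one possible reading, and 46% is an independence ceiling. At a 5% event rate the 12 tests give about 1% and the four three-group tests about 5%. An unconditional statement that the error rate is well above 5% is therefore not supported. Both replies stand and limit the point.

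The third reply is that the clinical success criteria under Follow up suggest a composite. They may, but the outcome table does not use it. The two lists also differ: the table has a gingival pocket item, while the criteria have swelling, inflammation and sinus tract.

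None of this removes the contradiction on the number of arms, or the excess for the named pair at event rates of 20% or more.

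**Conclusion.** The point holds in limited form. The contradiction on arm count and allocation ratio is certain from the text, as is the absence of a hypothesis or stated comparison for Group III.

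The error-rate part is conditional. For DDM versus blood clot over four signs, the false-positive risk is about 11–15% at true event rates of 20–40%, and under 5% at 10% or lower. With one three-group test per sign it is about 13–19% at 10–40%. If all 12 pairwise tests were run, it would be about 8–34% at 10–40%. These figures rest on assumed event rates, 10 evaluable teeth per arm and the uncorrected chi-square test. Fewer completers or a corrected test would change them.

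The null also spans radiographic outcomes. The figures cover only the four primary signs.

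**What to change.** - State three groups at 1:1:1 in the study design line, the Grouping sentence and the sample-size paragraph, where the per-group figure before dropout should agree with the total.
- Keep DDM versus blood clot as the single confirmatory comparison, on one primary outcome, at two-sided 0.05. One candidate is composite clinical success as defined by the criteria under Follow up. The outcome table and those criteria must then be made to list the same items.
- Add Group III to the aim and PICOTS as a secondary comparator.
- Report the Group III comparisons, the individual signs and the secondary outcomes as supportive, with estimates and confidence intervals.

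The cost is wording, plus the confirmatory status of the collagen comparisons and of the individual signs. The total of 30 is unchanged, because the confirmatory alpha stays at 0.05. The sizing rests on a standardised mean difference, so its power figure does not carry over to a binary composite. If the collagen comparisons are to stay confirmatory, alpha must be split, and at the protocol's own d the total rises to 39 or 42.
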